5.2.1.2 Dose Modification (Escalation/Titration/Other)

Adverse events (both non-serious and serious) associated with pembrolizumab exposure may represent an immunologic etiology. These adverse events may occur shortly after the first dose or several months after the last dose of treatment. Pembrolizumab must be withheld for drug-related toxicities and severe or life-threatening AEs as per Table 5 below. See dose modification and supportive care guideline sections, including use of corticosteroids. There are no dose reductions for pembrolizumab.

Dosing interruptions are permitted in the case of medical/surgical events or logistical reasons not related to study therapy (e.g., elective surgery, unrelated medical events, patient vacation, and/or holidays). Subjects should be placed back on study therapy within 3 weeks of the scheduled interruption. The reason for interruption should be documented in the patient's medical record.

Table 4. Dose Modification for Trametinib. Lowest permitted Trametinib dose will be 1.5 mg daily.

Dose Level	Trametinib Dose (QD) (D1-D10 administration unless otherwise specified)		
For Starting Dose	2 mg	1.5 mg	1.5 mg (dosed from D1-D7)
1 st Does Reduction	1.5 mg	1.5 mg (dosed from D1-D7)	Discontinue Trametinib
2 nd Dose Reduction	1.5 mg (dosed from D1-D7)	Discontinue trametinib	-

Table 5. Dose Modification Guidelines for Pembrolizumab (MK-3475) for Drug-Related Adverse Events

Toxicity	Hold Treatment For Grade	Timing for Restarting Treatment	Treatment Discontinuation
Diarrhea/Colitis	2-3	Toxicity resolves to Grade 0-1	Toxicity does not resolve within 12 weeks of last dose or inability to reduce corticosteroid to 10 mg or less of prednisone or equivalent per day within 12 weeks
	4	Permanently discontinue	Permanently discontinue
AST, ALT, or Increased	2	Toxicity resolves to Grade 0-1	Toxicity does not resolve within 12 weeks of last dose
Bilirubin	3-4	Permanently discontinue (see exception below) ^a	Permanently discontinue
Type 1 diabetes mellitus (if new onset) or	T1DM or 3-4	Hold pembrolizumab for new onset Type 1 diabetes mellitus or Grade 3-4 hyperglycemia	Resume pembrolizumab when patients are clinically and metabolically stable

Toxicity	Hold Treatment For Grade	Timing for Restarting Treatment	Treatment Discontinuation
Hyperglycemia		associated with evidence of beta cell failure	

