Hypophysitis	2-4	Toxicity resolves to Grade 0-1. Therapy with pembrolizumab can be continued while endocrine replacement therapy is instituted	Toxicity does not resolve within 12 weeks of last dose or inability to reduce corticosteroid to 10 mg or less of prednisone or equivalent per day within 12 weeks
Hyperthyroidism	3	Toxicity resolves to Grade 0-1	Toxicity does not resolve within 12 weeks of last dose or inability to reduce corticosteroid to 10 mg or less of prednisone or equivalent per day within 12 weeks
	4	Permanently discontinue	Permanently discontinue
Hypothyroidism		Therapy with pembrolizumab can be continued while thyroid replacement therapy is instituted	Therapy with pembrolizumab can be continued while thyroid replacement therapy is instituted
2 ^b T Infusion		Toxicity resolves to Grade 0-1	Permanently discontinue if toxicity develops despite adequate premedication
Reaction	3-4	Permanently discontinue	Permanently discontinue
Pneumonitis	neumonitis 2 Toxicity resolves to Grade 0-1		Toxicity does not resolve within 12 weeks of last dose or inability to reduce corticosteroid to 10 mg or less of prednisone or equivalent per day within 12 weeks
	3-4	Permanently discontinue	Permanently discontinue
Nephritis or inabi		Toxicity does not resolve within 12 weeks of last dose or inability to reduce corticosteroid to 10 mg or less of prednisone or equivalent per day within 12 weeks	
	3-4	Permanently discontinue	Permanently discontinue
All Other Drug- Related Toxicity ^c	3 or Severe	Toxicity resolves to Grade 0-1	Toxicity does not resolve within 12 weeks of last dose or inability to reduce corticosteroid to 10 mg or less of prednisone or equivalent per day within 12 weeks
	4	Permanently discontinue	Permanently discontinue

Note: Permanently discontinue for any severe or Grade 3 drug-related AE that recurs or any life-threatening event.

In case toxicity does not resolve to Grade 0-1 within 12 weeks after last infusion, trial treatment should be discontinued after consultation with the Sponsor Investigator. Subjects who require corticosteroids to manage drug-related adverse events must be at an equivalent dose of ≤10mg per day of prednisone to resume dosing with pembrolizumab. Furthermore, an inability to reduce

^a For patients with liver metastasis who begin treatment with Grade 2 AST or ALT, if AST or ALT increases by greater than or equal to 50% relative to baseline and lasts for at least 1 week then patients should be discontinued.

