Grade 2 (Intolerable) or Grade 3	Interrupt therapy until toxicity is grade 0-1 and reduce by one dose level when resuming therapy.
Grade 4	Discontinue permanently, or interrupt therapy until Grade 0 to 1 and reduce by one dose level when resuming therapy.

Please follow Table 5 and Table 6 for dose modifications unless specified below.

For Grade \geq 3 drug related adverse events attributed to trametinib both pembrolizumab and trametinib should be simultaneously interrupted with the exceptions shown below.

Except for Grade ≥ 3 lymphopenia

Exceptions where dose modifications are necessary for only trametinib:

- LVEF reduction
- Retinal Vein Occlusion (RVO) and Retinal Pigment Epithelial Detachment (RPED)

Table 7. Trametinib Dose Modification Guidelines and Stopping Criteria for LVEF Decrease

Clinical Evaluation	LVEF-drop (%) or CTCAE grade	Action and Dose Modification
Asymptomatic	Absolute decrease of >10% in LVEF compared to baseline and ejection fraction below the institution's LLN.	 Interrupt trametinib and repeat ECHO/MUGA within 2 weeks.^a If the LVEF recovers within 4 weeks (defined as LVEF ≥LLN and absolute decrease ≤10% compared to baseline): Consult with the Novartis trametinib medical monitor and request approval for restart. Restart treatment with trametinib at reduced dose by one dose level. Repeat ECHO/MUGA 2, 4, 8, and 12 weeks after restart; continue in intervals of 12 weeks thereafter. If LVEF does not recover within 4 weeks: Consult with cardiologist. Permanently discontinue trametinib. Report as SAE Repeat ECHO after 2, 4, 8, 12, and 16 weeks or until resolution.
Symptomatic ^b	 Grade 3: resting LVEF 39-20% or >20% absolute reduction from baseline Grade 4: Resting LVEF ≤20%. 	 Permanently discontinue trametinib. Report as SAE. Consult with cardiologist. Repeat ECHO/MUGA after 2, 4, 8, 12, and 16 weeks or until resolution.

^a If ECHO/MUGA does not show LVEF recovery after 2 weeks, repeat ECHO/MUGA 2 weeks later.

^b Symptoms may include: dyspnea, orthopenea, and other signs and symptoms of pulmonary congestion and edema.

Table 8. Trametinib Withholding and Stopping Criteria for QTc Prolongation

Prolongation*	Action and Dose Modification

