Uncomplicated Diarrhea, ¹ Grade 1 or 2	 Diet: Stop all lactose containing products; eat small meals, BRAT-diet (banana, rice, apples, toast) recommended. Hydration: 8-10 large glasses of clear liquids per day (e.g., Gatorade or broth). Loperamide³: Initially 4 mg, followed by 2 mg every 4 hours or after every unformed stool; maximum 16 mg/day. Continue until diarrhea- free for 12 hours. Diarrhea >24 hours: Loperamide 2 mg every 2 hours; maximum 16 mg/day. Consider adding oral antibiotics. Diarrhea >48 hours: Loperamide 2 mg every 2 hours; maximum 16 mg/day. Add budesonide or other second-line therapies (otreotide, or tincture of opium) and oral antibiotics. 	 Continue trametinib. If diarrhea is grade 2 for > 48h, interrupt trametinib until diarrhea resolves to grade ≤1. Restart trametinib at the same dose level If treatment delay is > 28 days, discontinue trametinib.
Uncomplicated Diarrhea, ¹ Grade 3 or 4 Any Complicated Diarrhea2	 Clinical evaluation mandatory. Loperamide³: Initially 4 mg, followed by 2 mg every 4 hours or after every unformed stool; maximum 16 mg/day. Continue until diarrhea- free for 12 hours. Oral antibiotics and second-line therapies if clinically indicated Hydration: Intravenous fluids if clinically indicated. Antibiotics (oral or intravenous) if clinically indicated. Intervention should be continued until the subject is diarrhea-free for ≥24 hours. Intervention may require hospitalization for subjects at risk of life- threatening complications. 	 Interrupt trametinib and pembrolizumab until diarrhea resolves to ≤ grade 1. Then restart pembrolizumab and trametinib reduced by one dose level.⁴ If 3 dose reductions of study treatment are clinically indicated, permanently discontinue trametinib. If treatment delay is >28 days, discontinue trametinib and pembrolizumab.

¹ Uncomplicated diarrhea defined by the absence of symptoms such as cramping, nausea/vomiting, ≥ grade 2, decreased performance status, pyrexia, sepsis, neutropenia ≥ grade 3, frank bleeding, and/or dehydration requiring intravenous fluid substitution

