² Complicated diarrhea defined by the presence of symptoms such as cramping, nausea/vomiting, ≥ grade 2, decreased performance status, pyrexia, sepsis, neutropenia ≥ grade 3, frank bleeding, and/or dehydration requiring intravenous fluid substitution. Patients with complicated diarrhea should be evaluated for pembrolizumab mediated autoimmune colitis with additional management as specified for pembrolizumab.

³ Loperamide should be made available prior to start of study treatment soloperamide administration can begin at the first signs of diarrhea.

⁴ Escalation of trametinib to previous dose level is allowed after consultation with the study chair and in the absence of another episode of complicated or severe diarrhea in the 4 weeks subsequent to dose reduction.

Table 13. Dose Modification Guidelines and Management for Rash

Rash Severity	Management Guideline	Dose Modification
Grade 1	 Initiate prophylactic and symptomatic treatment measures.¹ Use moderate strength topical steroid.² Reassess after 2 weeks. 	 Continue trametinib. If rash does not recover to baseline within 2 weeks despite best supportive care, reduce trametinib by one dose level.³
Grade 2	 Initiate prophylactic and symptomatic treatment measures.¹ Use moderate strength topical steroid.² Reassess after 2 weeks. 	 Reduce trametinib by one dose level. If rash recovers to ≤ grade 1 within 2 weeks, increase dose to previous dose level. If no recovery to ≤ grade 1 within 2 weeks, interrupt trametinib until recovery to ≤ grade 1. Restart trametinib at reduced dose level.
Grade ≥3	 Use moderate strength topical steroids. Consider oral methyl- prednisolone dose pack.² Consider consulting dermatologist. 	 Interrupt trametinib until rash recovers to ≤ grade 1. Then restart pembrolizumab and trametinib (reduced by one dose level).³ If no recovery to ≤ grade 2 within 4 weeks, permanently discontinue trametinib and pembrolizumab.

Rash prophylaxis is recommended for the first 6 weeks of study treatment.

Moderate-strength topical steroids: Hydrocortisone 2.5% cream or fluticasone priopionate 0.5% cream. Trametinib may be escalated to previous dose level if no rash is evident 4 weeks after restarting study treatment.

Table 14. Pneumonitis Guidelines

CTCAE Grade	Adverse Event Management	Action and Dose Modification

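### For a Grade 4 rash that pembrolizumab may have caused, or whose cause is mixed or unclear, Table 5 stops pembrolizumab for good while Table 13 restarts it after recovery

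*Combined protocol and SAP*

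**What the plan says.** All the dosing rules at issue are in Section 5.2.1.2.

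- **Table 5 (pembrolizumab).** The text before it says "Pembrolizumab must be withheld for drug-related toxicities and severe or life-threatening AEs as per Table 5 below". Grade 4 diarrhea/colitis is a permanent stop. Rash has no row of its own and falls under the residual row for other drug-related toxicity, where Grade 4 is also a permanent stop. The note below the table reads "Permanently discontinue for any severe or Grade 3 drug-related AE that recurs or any life-threatening event".
- **Table 6 (trametinib), Grade 4.** "Discontinue permanently, or interrupt therapy until Grade 0 to 1 and reduce by one dose level when resuming therapy".
- **Precedence.** After Table 6: "Please follow Table 5 and Table 6 for dose modifications unless specified below".
- **Joint interruption.** The next sentence says that Grade 3 or higher events attributed to trametinib lead to interruption of both drugs. A short list follows, introduced by "Exceptions where dose modifications are necessary for only trametinib", naming LVEF reduction and two retinal events.
- **Table 13, rash of Grade 3 or higher.** Trametinib is interrupted until the rash is Grade 1 or less. "Then restart pembrolizumab and trametinib (reduced by one dose level"). Both drugs stop permanently only if the rash has not improved to Grade 2 or less within 4 weeks.
- **Table 12, Grade 3 or 4 uncomplicated diarrhea and any complicated diarrhea.** Both drugs are interrupted until Grade 1 or less. "Then restart pembrolizumab and trametinib reduced by one dose level". Both stop if the delay exceeds 28 days. Footnote 2 adds "Patients with complicated diarrhea should be evaluated for pembrolizumab mediated autoimmune colitis with additional management as specified for pembrolizumab".

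Table 20 (Section 7.2.4) describes Grade 4 as life-threatening.

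**The concern.** Tables 13 and 12 do not separate Grade 4 from Grade 3 and do not refer back to Table 5's Grade 4 stop. Read with the precedence sentence, they allow pembrolizumab to be resumed after an event for which Table 5 ends it. Two sites could each follow the protocol and do opposite things after the same life-threatening rash, and the riskier course is the one that the precedence wording supports. The trial is multisite (Appendix 11.1), and safety and tolerability are its primary objective (Section 3.1). What is at stake is patient safety and uniform conduct, not the analysis.

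**Working it through.** The plan gives no figure to reproduce. The check sets the pembrolizumab instructions side by side.

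| Event, Grade 4 | Table 5 | Event-specific table | Result under the precedence sentence |
|---|---|---|---|
| Rash | Permanent stop (residual row and note) | Table 13: restart after recovery to Grade 1 or less | Restart |
| Uncomplicated diarrhea | Permanent stop (diarrhea/colitis row and note) | Table 12: restart after recovery to Grade 1 or less | Restart |
| Complicated diarrhea | Permanent stop | Table 12: same row, but footnote 2 adds pembrolizumab-specific management | Returned to the pembrolizumab rules |
| Pneumonitis | Permanent stop | Table 14: permanent stop of both drugs | No conflict |

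**Does attribution settle it?**

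1. *Attributed to trametinib.* The joint-interruption sentence prescribes interruption of both drugs at Grade 3 or higher. It does not prescribe a permanent pembrolizumab stop. Table 13's restart fits that rule, so one coherent instruction exists.
2. *Possibly caused by pembrolizumab, mixed or unclear.* The joint-interruption sentence does not clearly apply. Table 5 says stop. Table 13 carries no attribution limit, names pembrolizumab and says restart. This conflict remains.
3. *Clearly caused by pembrolizumab.* Section 5.6.3 says that the rash guidance derives from experience with MEK and EGFR inhibitors, so a reader may go to Table 5. Table 13 itself does not say so.

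**How often?** The documents give no rate, so everything here except n is an assumption. Let p be the per-patient rate of Grade 4 rash or uncomplicated Grade 4 diarrhea (0.5%, 1%, 2%). Let r be the share that recovers to Grade 1 or less, reaches a pembrolizumab restart decision and falls within the conflict (25%, 50%, 100%; the last is an upper bound). With n = 42, the planned evaluable total in Section 1.0, and q = p × r:

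P(at least one) = 1 − (1 − q)^42; expected number = 42q.

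| p | r = 25% | r = 50% | r = 100% |
|---|---|---|---|
| 0.5% | 5% | 10% | 19% |
| 1% | 10% | 19% | 34% |
| 2% | 19% | 34% | 57% |

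For example, p = 1% and r = 50% give q = 0.005, 1 − 0.995^42 = 0.190, and 42 × 0.005 = 0.21 patients. Across the grid the expected number runs from 42 × 0.00125 = 0.05 to 42 × 0.02 = 0.84.

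**The case against.** The best defense is that Table 5 governs events from pembrolizumab and Tables 12 and 13 govern events from trametinib. The paragraph introducing Table 5 opens with events linked to pembrolizumab exposure, and the joint-interruption sentence gives trametinib-attributed events their own rule. This stands for events attributed to trametinib. A reader might infer that every recovered Grade 4 rash or diarrhea is caught in a contradiction, or that rash falls under Table 5's stop because it is missing from the trametinib-only list. The documents do not support either reading: being off that list means only that pembrolizumab is held as well. The defense does not reach mixed or unclear cases, because neither event-specific table limits its restart by attribution.

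A second defense is oversight. The rechallenge note in Table 20 requires advance Sponsor-Investigator approval after a serious event that pembrolizumab may have caused, or whenever re-exposure poses additional significant risk. A reader might infer that a trametinib-attributed event escapes this check. It need not, because the second condition has no attribution test. Serious events also reach the Sponsor Investigator within 24 hours (Section 7.2.3.1) and are discussed across centers (Section 10.5). These controls make unsupervised divergence less likely. They do not decide the question, because approval is to follow the dose modification guidelines, which are the texts in conflict. The rule ending pembrolizumab when a serious event recurs acts only after re-exposure.

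Third, Table 5's Grade 4 stop is not universal. Its own rows allow resumption after Grade 4 hypophysitis and after Grade 3–4 hyperglycemia, and a later paragraph of Section 5.2.1.2 provides for patients who continue pembrolizumab after a Grade 4 event. That is correct, but it adds ambiguity for rash and does not cancel the residual row.

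Fourth, if precedence is taken literally there is one rule, and the restart is a design choice. Nothing shows that overriding the life-threatening stop was intended, and Table 14 keeps that stop for pneumonitis.

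Finally, diarrhea deserves little weight. Footnote 1 to Table 12 excludes dehydration needing intravenous fluids, sepsis, bleeding and reduced performance status, so life-threatening diarrhea would almost always be complicated.

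**Conclusion.** The point holds as a minor safety-wording correction. The protocol gives opposite pembrolizumab instructions for a Grade 4 rash that pembrolizumab may have caused, or whose attribution is mixed or unclear, and its precedence sentence favors the restart. Uncomplicated Grade 4 diarrhea is a secondary note with the same wording conflict. The approval requirement reduces the problem without resolving it.

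The textual conclusion needs no numerical assumption. The frequencies rest entirely on assumed p and r and show only that the expected count stays below one patient over the range tried. Sample size and error rates are unaffected.

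**What to change.** 1. Split Table 13's row for Grade 3 or higher. Grade 3 keeps the present rule. At Grade 4, discontinue pembrolizumab permanently per Table 5 unless the event is attributed to trametinib alone. In that case interrupt both drugs and restart pembrolizumab only with documented advance Sponsor-Investigator approval. Handle trametinib by Table 6's Grade 4 rule.
2. Make the same split in Table 12.
3. Add to the precedence sentence that the event-specific tables do not override Table 5's stop for Grade 4 or life-threatening events, except as stated.
4. Align the later paragraph on continuing pembrolizumab after a Grade 4 event. Limit it to events for which Table 5 allows resumption, such as hypophysitis or hyperglycemia, or to the approved exception.

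The cost is amendment wording: two table rows and two sentences, with no change to design or analysis. The clinical downside is that the rare patient with a recovered Grade 4 rash or diarrhea not attributed to trametinib alone could not resume pembrolizumab.

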b If symptoms resolve within one hour of stopping drug infusion, the infusion may be restarted at 50% of the original infusion rate (e.g., from 100 mL/hr to 50 mL/hr). Otherwise dosing will be held until symptoms resolve and the subject should be premedicated for the next scheduled dose; Refer to Table 3 – Infusion Treatment Guidelines for further management details.

^c Patients with intolerable or persistent Grade 2 drug-related AE may hold study medication at physician discretion. Permanently discontinue study drug for persistent Grade 2 adverse reactions for which treatment with study drug has been held, that do not recover to Grade 0-1 within 12 weeks of the last dose.

the corticosteroid dose for managing a drug-related adverse event to the equivalent of \leq 10 mg prednisone per day within 12 weeks of last pembrolizumab dose should result in permanent discontinuation from pembrolizumab. With investigator and Sponsor Investigator agreement, subjects with a laboratory adverse event still at Grade 2 after 12 weeks may continue treatment in the trial only if asymptomatic and controlled. For information on the management of adverse events, see Section 5.7.2.

In subjects who continue on pembrolizumab having experienced a Grade 3, Grade 4, or persistent (> 4 weeks) Grade 2 drug-related AE, once the subject has recovered from the AE to Grade 0-1, the dosing interval in subsequent cycles may be increased by 1 week (e.g., to every 4 week dosing in subjects who were on an every 3 week schedule). However, in subjects who experience Grade 3 or 4 pneumonitis, or recurrent persistent (>4 weeks) Grade 2 drug - related pneumonitis after rechallenge from a prior episode of persistent (> 4 weeks) Grade 2 drug-related pneumonitis, pembrolizumab must be permanently discontinued.

For subjects who experience a recurrence of the same AE(s) at the same grade or greater with rechallenge of pembrolizumab, a consultation between the Sponsor Investigator and investigator should occur to determine whether the subject should continue in the trial. However, for a subject who experiences a recurrence of the same serious adverse event at the same grade or greater with rechallenge of pembrolizumab, the subject must discontinue pembrolizumab.

Table 6 Dose Modification Guidelines for Trametinib for Drug-Related Adverse Events (Unless Otherwise Specified)

Grade (CTC-AE)*	Dose Modifications
Grade 1 or Grade 2 (Tolerable)	Continue treatment and monitor as clinically indicated.

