Grade 1	 CT scan (high-resolution with lung windows) recommended. Work-up for infection. Monitoring of oxygenation via pulse- oximetry recommended. Consultation with pulmonologist recommended. 	Continue trametinib at current dose.
Grade 2	 CT scan (high-resolution with lung windows). Work-up for infection. Consult pulmonologist. Pulmonary function tests: If < normal, repeat every 8 weeks until ≥ normal. Bronchoscopy with biopsy and/or BAL recommended. Symptomatic therapy including corticosteroids if clinically indicated. 	 Interrupt trametinib and pembrolizumab until recovery to grade ≤1. If AE resolved to Grade ≤1 and relationship to trametinib and or pembrolizumab is equivocal, restarting pembrolizumab and trametinib (with dose reduction at investigators discretion) may be considered, after discussion with the study chair. If treatment delay is > 4 weeks, permanently discontinue trametinib and pembrolizumab.
Grade 3	 CT scan (high-resolution with lung windows). Work-up for infection. Consult pulmonologist. Pulmonary function tests-if < normal, repeat every 8 weeks until ≥ normal. Bronchoscopy with biopsy and/or BAL if possible. Symptomatic therapy including corticosteroids as clinically indicated. 	Permanently discontinue trametinib and pembrolizumab.
Grade 4	• Same as grade 3.	Permanently discontinue trametinib and pembrolizumab.

Dose Reduction Scheme for Trametinib

No dose reductions for trametinib are permitted below 1.5 mg PO daily.

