5.6 Rescue Medications & Supportive Care

5.6.1 Supportive Care Guidelines

5.6.2 Pembrolizumab

Subjects should receive appropriate supportive care measures as deemed necessary by the treating investigator. Suggested supportive care measures for the management of adverse events

with potential immunologic etiology are outlined below. Where appropriate, these guidelines include the use of oral or intravenous treatment with corticosteroids as well as additional anti-inflammatory agents if symptoms do not improve with administration of corticosteroids. Note that several courses of steroid tapering may be necessary as symptoms may worsen when the steroid dose is decreased. For each disorder, attempts should be made to rule out other causes such as metastatic disease or bacterial or viral infection, which might require additional supportive care. The treatment guidelines are intended to be applied when the investigator determines the events to be related to pembrolizumab.

Note: if after the evaluation the event is determined not to be related, the investigator does not need to follow the treatment guidance (as outlined below). Refer to Section 5.2.1 for dose modification.

It may be necessary to perform conditional procedures such as bronchoscopy, endoscopy, or skin photography as part of evaluation of the event.

• Pneumonitis:

- For Grade 2 events, treat with systemic corticosteroids. When symptoms
 improve to Grade 1 or less, steroid taper should be started and continued over no
 less than 4 weeks.
- o For **Grade 3-4 events**, immediately treat with intravenous steroids. Administer additional anti-inflammatory measures, as needed.
- Add prophylactic antibiotics for opportunistic infections in the case of prolonged steroid administration.

• Diarrhea/Colitis:

Subjects should be carefully monitored for signs and symptoms of enterocolitis (such as diarrhea, abdominal pain, blood or mucus in stool, with or without fever) and of bowel perforation (such as peritoneal signs and ileus).

- O All subjects who experience diarrhea/colitis should be advised to drink liberal quantities of clear fluids. If sufficient oral fluid intake is not feasible, fluid and electrolytes should be substituted via IV infusion. For Grade 2 or higher diarrhea, consider GI consultation and endoscopy to confirm or rule out colitis.
- o For Grade 2 colitis, administer oral corticosteroids.
- For Grade 3 or 4 colitis, treat with intravenous steroids followed by high dose oral steroids.

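### Restart and stopping instructions for Grade 2 pneumonitis do not agree: Table 14 conflicts with the Section 5.2.1.2 rechallenge text, and the precedence sentence settles only the Table 5 row

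*Combined protocol and SAP*

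**What the plan says.** Four places in the combined protocol and SAP bear on Grade 2 pneumonitis.

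- **Section 5.2.1.2, Table 14 (Grade 2 row).** Both drugs are interrupted until the event is Grade 1 or less. The restart route it sets out begins "If AE resolved to Grade ≤1 and relationship to trametinib and or pembrolizumab is equivocal"; restarting may then be considered after discussion with the study chair. The row ends: "If treatment delay is > 4 weeks, permanently discontinue trametinib and pembrolizumab".
- **Section 5.2.1.2, Table 5 (pneumonitis row, Grade 2).** Pembrolizumab is held until Grade 0-1. The ground for discontinuing is "Toxicity does not resolve within 12 weeks of last dose or inability to reduce corticosteroid to 10 mg or less of prednisone". The steroid condition carries the same 12-week limit.
- **Section 5.2.1.2, running text between Tables 5 and 6.** Patients who stay on pembrolizumab after certain drug-related events, including a Grade 2 event persisting more than 4 weeks, may have the dosing interval lengthened once they recover. An exception follows for Grade 3-4 pneumonitis and for recurrent persistent Grade 2 pneumonitis "after rechallenge from a prior episode of persistent (> 4 weeks) Grade 2 drug-related pneumonitis, pembrolizumab must be permanently discontinued".
- **Section 5.6.2, pneumonitis.** "For Grade 2 events, treat with systemic corticosteroids", with a taper of at least 4 weeks once symptoms improve to Grade 1 or less. Table 14 leaves corticosteroids to clinical indication.

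A precedence sentence stands after Table 6 and before Tables 7 to 14: "Please follow Table 5 and Table 6 for dose modifications unless specified below". The opening of Section 5.2.1.2 sends the reader to Table 5 for withholding pembrolizumab. The running text sends the reader to Section 5.7.2 for adverse event management.

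**The concern.** The stop in the running text is triggered by a second persistent episode after rechallenge. It has a purpose only if some patients resume pembrolizumab after a first drug-related Grade 2 pneumonitis that lasted more than 4 weeks. Table 14 describes restart for an equivocal relationship and stops both drugs when the delay passes 4 weeks. An investigator who follows the running text and one who follows Table 14 can reach opposite decisions on the same patient.

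Pneumonitis is a serious lung toxicity, and safety and tolerability is the primary objective (Section 3.1). Section 11.1 describes multisite registration, so sites could handle the same event differently. Discontinuation and later-cycle toxicity feed into the tolerability judgement: Section 5.4 lets toxicity in later cycles lower the RP2D, and Section 8.0 makes acceptable tolerability a condition for recommending a sequence.

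**Working it through.** The plan states no figure to reproduce. The check is a comparison of the text, then calendar arithmetic.

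**Step 1. Which conflicts does the precedence sentence settle?** It names Tables 5 and 6 as the defaults and yields to what follows. Table 14 follows, concerns pneumonitis and names both drugs, so it displaces the Table 5 pneumonitis row. The rechallenge text is in neither table and stands above the sentence, so nothing ranks it against Table 14.

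**Step 2. The conflict that does not depend on any clock.**

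| Place | Which event may be followed by resumption |
|---|---|
| Table 14, Grade 2 | Recovered to Grade 1 or less, relationship equivocal |
| Table 5, Grade 2 row | Drug-related event (the table's scope), recovered to Grade 0-1 |
| Running text | Drug-related Grade 2 pneumonitis, even if it lasted more than 4 weeks |

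For a clearly drug-related episode, Table 14 sets out no restart route, while the running text assumes one.

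**Step 3. The time limits.** Inputs: pembrolizumab every 21 days (Section 5.2.1.1); 4 weeks = 28 days (Table 14); 12 weeks = 84 days (Table 5). Put the last pembrolizumab dose on day 0, so the next is due on day 21. Table 14 does not say when treatment delay starts, so two assumptions are shown.

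| Start of delay (assumed) | Table 14 limit | Table 5 limit | Difference | Ratio |
|---|---|---|---|---|
| Last dose, day 0 | 0 + 28 = day 28 | day 84 | 84 - 28 = 56 days (8 weeks) | 84/28 = 3.0 |
| Missed dose, day 21 | 21 + 28 = day 49 | day 84 | 84 - 49 = 35 days (5 weeks) | 84/49 = 1.7 |

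**Step 4. Can an episode over 4 weeks fit within Table 14's delay limit?** The running text counts episode duration and Table 14 counts delay.

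- Delay from the missed dose: with onset on day 10 (after the last trametinib dose of a D1-D10 course) and resolution on day 44, the episode lasts 44 - 10 = 34 days and is persistent. The delay is 44 - 21 = 23 days, inside the limit. An episode starting just after day 0 could last up to about 49 days (7 weeks) and still fit.
- Delay from the last dose: an episode that starts after day 0 and lasts more than 28 days ends after day 28, so it never fits.

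The time conflict is therefore complete under one reading and partial under the other.

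**Step 5. Corticosteroids.** Section 5.6.2 introduces its measures as suggestions, for events that the investigator attributes to pembrolizumab. Table 14 also covers events attributed to trametinib or of uncertain cause. The two can coexist. The taper of at least 4 weeks sits close to a 4-week delay limit, but resuming pembrolizumab depends on being at 10 mg per day or less of prednisone equivalent (Section 5.2.1.2), not on a finished taper.

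**Step 6. Cross-references.** Neither the opening of Section 5.2.1.2 nor the Table 5 row mentions Table 14. Section 5.7.2 is the contraception section; supportive care for pembrolizumab is in Section 5.6.2.

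**The case against.** The strongest reply is that the document has its own hierarchy: defaults in Tables 5 and 6, specific guidance below. That stands for the Table 5 row. A reader might infer two limits of equal rank, 4 and 12 weeks, and the precedence sentence does not support that. What remains of Table 5 is a row that is displaced without saying so.

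The second reply is that the running text grants nothing. It adds a mandatory stop, and stopping rules can accumulate without contradiction. This is partly right: the text does not say that pembrolizumab stops solely on a recurrence, and the 12-week grounds apply as well. But a stop conditional on rechallenge after a persistent drug-related episode presupposes that such a rechallenge can happen, and Table 14 does not provide for it when the relationship is clear. One could read Table 14's interruption until recovery as implying resumption on its own. The restart condition that follows would then have no function, so the ambiguity remains.

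Third, a reader might infer that rechallenge after an episode over 4 weeks is impossible under Table 14, or that the limits simply differ three-fold. The clocks differ, and both statements hold only if delay is counted from the last dose.

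Fourth, no effect on the results is shown. The documents give no frequency of Grade 2 pneumonitis, and the DLT criteria in Section 5.4 do not refer to either limit. That stands.

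**Conclusion.** The point holds as an inconsistency in the restart and stopping instructions for Grade 2 pneumonitis. The core is the clash between the rechallenge text and Table 14 for a clearly drug-related episode; it does not depend on how delay is counted, and the precedence sentence does not resolve it. The time limits add to it: between Table 14's limit and day 84 there are 5 to 8 weeks in which a reader sent to Table 5 would act differently from a reader of Table 14. That range rests on the 21-day cycle and the two assumed starting points.

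The corticosteroid difference is minor. A reader might infer that Section 5.6.2 obliges a steroid course that cannot fit within Table 14; its measures are suggestions, and resumption does not wait for the end of the taper.

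A change in the RP2D or in discontinuation rates is possible but not demonstrated. For scale, with 12 patients per expansion arm (Section 5.3), one patient handled differently moves that arm's discontinuation proportion by 1/12 = 8.3 percentage points. The case for acting is patient safety and uniform handling across sites, at low cost.

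**What to change.** Reconcile Table 5, the rechallenge text in Section 5.2.1.2, Table 14 and Section 5.6.2 for Grade 2 pneumonitis. The amendment should:

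- state which passage governs each drug, and extend the precedence sentence or reword the running text so that the two are ranked;
- make the instructions agree on whether and when treatment may resume after a drug-related episode as well as an equivocal one;
- define when treatment delay starts, for each drug if needed, and how it relates to time from last dose and episode duration;
- align the corticosteroid wording, or state when each version applies;
- point from the opening of Section 5.2.1.2 and from the Table 5 row to Table 14, and correct the reference to Section 5.7.2.

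The clinical team decides the content; this review takes no view on which limit or restart condition is right. The cost is a small wording amendment, with no change to design, sample size or analysis.
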